# 3. STUDY DESIGN

This is a global, multi-centre, long-term, prospective, observational study to evaluate treatment patterns and clinical outcomes in patients with advanced or metastatic RCC treated for the first time with pazopanib. The study is designed to enroll approximately 700-1000 patients in over the course of an enrollment period of approximately 18 months. Sites will be contacted and qualified by the estimated number of advanced or metastatic RCC patients available for enrollment annually. To the extent possible, consecutive patients meeting inclusion/exclusion criteria will be enrolled. Sites will be required to maintain a patient enrolment log of eligible patients at their treatment centres. This log will document how patients came to be included or excluded from the study, in order to assess the representativeness of the study population. The overall number of patients and sites may be adjusted during the study to meet enrollment goals, if needed. Eligible patients will be enrolled by medical oncologists and potentially by urologists experienced in the management of patients with RCC, if consistent with local practice.

There are no protocol—mandated visits or procedures associated with the study. Each patient is expected to participate for a maximum of 30 months or until premature discontinuation (i.e., due to death, withdrawal of consent, lost to follow-up or study termination). Patient completion is defined in Section 4. Follow-up information will be collected approximately every 3 months (a window of  $\pm$  4 weeks around the date of the suggested data collection will be allowed). If the patient is not seen for a regularly scheduled visit at that time, the site may contact the patient by telephone to solicit information regarding the events of interest and to limit loss to follow up. It is anticipated that frequency of patient assessment and imaging will differ according to local standard practice; therefore the quarterly data collection time points are intended to collect all assessments (with the date of assessment) since the previous visit date.

Supplementary study conduct information not mandated to be present in this protocol is provided in the accompanying Study Procedures Manual (SPM). The SPM will provide the site personnel with administrative and detailed technical information that does not impact patient safety.

# 3.1. Discussion of Design

Due to the need to have evaluable and comparable patients, the patient populations included in clinical trials are by design more restricted than those patients who will receive a therapy within a clinical setting. While clinical trials provide crucial information regarding the efficacy and safety of the drug, observational data can extend and augment what is known, including identifying optimal regimens and optimal therapies for special populations of patients (e.g., elderly patients, poor risk patients) who are unlikely to be adequately represented in clinical trials. In addition, real world data may help elucidate which patients might respond best to a particular therapy and may help in monitoring the benefits of a particular therapy throughout the treatment course.

# 4. PATIENT SELECTION AND DISCONTINUATION/COMPLETION CRITERIA

#### 4.1. Patient Selection Criteria

#### 4.1.1. Number of Patients

Approximately 700-1000 patients will be enrolled. See Section 9.1.1 for sample size assumptions.

#### 4.1.2. Inclusion Criteria

Specific information regarding warnings, precautions, contraindications, adverse events, and other pertinent information regarding pazopanib that may impact patient treatment is found in the local product labeling.

Deviations from inclusion criteria are not allowed because they can potentially jeopardize the scientific integrity of the study. Therefore, adherence to the criteria as specified in the protocol is essential.

Patients eligible for enrolment in the study must meet all of the following criteria:

- Age  $\geq$  18 years at enrollment
- Documented diagnosis of advanced and/or metastatic clear cell or predominantly clear cell RCC
- Clinical decision made to initiate treatment with pazopanib prior to enrollment in the study, but within 30 days of enrollment
- Willing and able to provide written informed consent

#### 4.1.3. Exclusion Criteria

Deviations from exclusion criteria are not allowed because they can potentially jeopardize the scientific integrity of the study. Therefore, adherence to the criteria as specified in the protocol is essential.

Patients meeting any of the following criteria must not be enrolled in the study:

- Patients currently participating in any interventional clinical trials in which treatment regimen and/or monitoring is dictated by a protocol
- Previous exposure to an investigational or licensed multi-kinase inhibitor or an anti-VEGF angiogenesis inhibitor for advanced or metastatic disease (for guidance, refer to Appendix 1)
- Life expectancy < 12 weeks

# 4.2. Permanent Discontinuation from Study Treatment and Patient Completion Criteria

# 4.2.1. Permanent Discontinuation from Study Treatment

Patients will receive pazopanib at the discretion of the treating physician (e.g., until disease progression, death or unacceptable adverse event). The primary reason study treatment was permanently discontinued must be documented in the eCRF.

If the patient voluntarily discontinues from treatment due to toxicity, 'adverse event' should be recorded as the primary reason for permanent discontinuation in the eCRF.

All patients who permanently discontinue study treatment should be followed for progression, survival and new therapies according to the protocol schedule, for up to 30 months post-enrollment.

## 4.2.2. Patient Completion

A patient will be considered to have completed the study if the patient dies during the study treatment or follow-up period or has been in follow-up for 30 months, whichever is sooner. Document the cause of death in the eCRF. A patient will be considered to have withdrawn from the study if the patient has not died and is lost to follow-up, has withdrawn consent, at the investigator's discretion is no longer being followed or if the study is closed/terminated.

#### 5. STUDY TREATMENT

The term 'study treatment' is used throughout the protocol to describe any combination of products received by the patient as per the protocol design. Study treatment may therefore refer to the individual study treatments or the combination of those study treatments

# 5.1. Guidelines for Events of Special Interest and Dose Modifications

Guidance for dose modifications and interruptions for management of common toxicities associated with the study treatment is included in the product local labeling for pazopanib.

# 5.2. Relative Dose Intensity

All pazopanib dose changes, interruptions and discontinuations will be collected as part of this observational study.

Relative dose intensity (RDI) is a quantification of how closely an administered course of chemotherapy adheres to the intended regimen. Dose intensity can be increased or decreased through altering dose administered, time interval of administration, or both. For the purposes of this study, RDI will be calculated as the ratio of average daily dose of pazopanib to the recommended daily dose of pazopanib. During the pazopanib Phase III registration trial [VEG105192], the mean RDI was 0.86 (standard deviation 0.26).

# 6. CONCOMITANT MEDICATIONS AND NON-DRUG THERAPIES

As a long-term, observational study to evaluate treatment patterns and outcomes in patients treated in the post-marketing setting, no restrictions on concomitant treatments are associated with the study over and above those recommended in the regulatory authorisation. Investigators will be asked to record exposure to any concomitant treatments (within 6 weeks of initiating treatment with pazopanib and throughout follow-up) that are categorized as a CYP3A4 inhibitor or a CYP3A4 inducer.

#### 7. STUDY ASSESSMENTS AND PROCEDURES

A signed, written informed consent form must be obtained from the patient prior to any study-specific procedures or assessments. The web-based data collection, or Electronic Data Capture (EDC) system will comply with 21 CFR Part 11 regarding electronic records. All sites will be trained in the proper use of the EDC system as part of any site initiation visit or other activities prior to patient enrollment at the site. Once trained, physician and site personnel will be able to access their account with a username and password. The data collection is designed to minimise the burden on the participating physicians and patients, and maximise site and patient retention. Structured questionnaires, and the resultant electronic case report form (eCRF) for data entry, are designed to elicit the specific desired data points. During the baseline visit, the site will be instructed to obtain additional information regarding the patient, including secondary contact information for use in the event the site cannot reach the patient.

Refer to the Time and Events Table for the timing of all assessments (Table 1). Details on effectiveness and safety assessments are presented in Section 7.3 and Section 7.4, respectively. Further details of study procedures and assessments can be found in the study procedures manual (SPM). Basic site and investigator level data will be collected in order to characterize the sites (e.g., practice type, practice size).

Procedures conducted as part of the patient's routine clinical management (e.g., blood count, imaging study) and obtained prior to signing of informed consent should be utilized for determining eligibility and baseline purposes.

Table 1 Table of Recommended Assessments [Time and Events]

	Baseline	Every 3 months (± 4 weeks)	Early discontinuation
Inclusion/exclusion	Х		
Demography	Х		
Patient height & weight	Χ		
RCC disease history	Χ		
RCC treatment history	Χ		
MSKCC risk category, if recorded	X		
Medical history/concomitant conditions	X	X	X
Performance status (ECOG and Karnofsky score), if recorded	Х	Х	
Pazopanib exposure	Xa	Χ	Х
Exposure to select concomitant medications	X	X	X
Select laboratory testing (if performed)	Х	Х	X
Evidence of radiographic and or clinical progression		Х	Х
Additional treatments for RCC		Χ	Χ
HRQoL [EQ-5D, FKSI-19 and FACIT Fatigue scale] b	Х	Х	Х
Adverse events (SAEs and AESIs) c	X		> X
Reason for discontinuation (if applicable)			Х

a. Only for patients who have received their first dose within 30 days prior to enrollment

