# 2. OBJECTIVES AND ENDPOINTS

Objectives	Endpoints
Primary	
The primary objectives of the study are:	
To evaluate overall survival (OS), progression-free survival (PFS) and the overall response rate (ORR) in patients treated with pazopanib	PFS: defined as the interval between the date of first treatment with pazopanib and the earliest date of disease progression (by tumour response assessed by imaging or by clinical deterioration, whichever comes first) or death due to any cause OS: defined as the time from first treatment with pazopanib until death due to any cause ORR: defined as the percentage of patients with documented response (CR or PR) at any time during follow-up
2. To characterize the relative dose intensity (RDI) and its observed effect on treatment outcomes	Study population distribution of RDI
3. To characterise the RCC patient population treated with pazopanib (e.g., by demographics, disease characteristics, previous RCC treatment history) in comparison to a selected clinical trial population	Study population distribution of baseline characteristics
To evaluate the change in health-related quality of life (HRQoL) relative to baseline in patients treated with pazopanib	Change from baseline
5. To evaluate the frequency of serious adverse events (SAEs) and adverse events of special interest (AESIs) in patients treated with pazopanib	Any adverse event that results in a pazopanib dose modification or discontinuation Evidence of liver toxicity (e.g., increased ALT and/or AST, liver failure) New onset or worsened hypertension Cardiac dysfunction (e.g., decreased left ventricular function, congestive heart failure) Thyroid dysfunction
Secondary	
1.To evaluate clinical effectiveness, safety and RDI in those patients with comparable baseline characteristics to those included in the Phase III clinical trial [VEG105192]	Same as primary effectiveness, safety and RDI objectives.
2. To evaluate clinical effectiveness, safety, RDI and HRQoL in relevant subgroups treated with pazopanib	Same as primary effectiveness, safety, HRQoL and RDI objectives.

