## 7.1. Baseline Assessments

## 7.1.1. Baseline Data

Baseline data collection will include:

- Demographics (date of birth, sex, race/ethnicity)
- Weight, Height (calculated BMI)
- Medical history (including cardiovascular, hepatic, endocrine, secondary malignancies, renal including presence of hereditary RCC syndromes)
- RCC history, including:
  - Date of initial RCC diagnosis

b. Applicable only to sites where HRQoL questionnaires may be administered

c. Refer to Section 7.4 regarding details of the timing and nature of events to be reported.

- Date of diagnosis with advanced/metastatic RCC
- Site of metastases (lung, bone, liver, adrenal glands, CNS, lymph nodes, other)
  - Number of metastatic sites
  - Existence of measurable lesions (yes/no)
  - Whether disease status evaluation conducted as part of routine care was consistent with RECIST methods (yes/no)
- Metastasis confirmed by imaging (type, date) and by biopsy (yes/no, date)
- Other histopathology: sarcomatoid features, microvascular invasion, tumour necrosis, and invasion of the collecting system
- RCC treatment history
  - Surgical history (simple, radical or partial nephrectomy; arterial embolization; metastatic lesion resection), dates, status post-surgery
  - Radiation therapy, stereotactic radiotherapy
  - Radiofrequency or cryo-ablation
  - Previous lines of systemic therapy, including immunotherapy (e.g., interferon  $\alpha$ , IL-2)
- Performance status (ECOG and Karnofsky scales, included in Appendix 3) at enrollment, if recorded
- MSKCC and/or modified Heng risk category at enrollment (favourable/good, intermediate or poor), if recorded (for description, refer to Appendix 3)
- Initial pazopanib prescription
- Pazopanib start date
- Any changes to pazopanib dose or regimen since starting, with dates and dose changes, duration of interruption (if applicable)
- Selected concomitant medications (CYP3A4 inhibitors and inducers)
- Relevant laboratory testing (e.g., haemoglobin, platelet count, LDH, AST, ALT)
- HRQoL [EQ-5D, FKSI-19 and FACIT Fatigue scale, refer to Section 7.5], where applicable
- Occurrence of any SAEs/AESIs since starting pazopanib

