#### 7.3. Effectiveness

#### 7.3.1. Effectiveness Endpoints

The primary effectiveness endpoints of this study are:

- Overall survival (OS): defined as the time from first treatment with pazopanib until death due to any cause;
- Progression free survival (PFS): defined as the interval between the date of first treatment with pazopanib and the earliest date of disease progression (by tumour response assessed by imaging or by clinical deterioration, whichever comes first) or death due to any cause;
- Overall Response Rate (ORR): defined as the percentage of patients with documented response [complete response (CR) or partial response (PR)] at any time.

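### Patients may enrol up to 30 days after first dose, so baseline HRQoL can be an on-treatment value, risk factors may be post-dose, and OS and PFS carry a modest upward immortal-time bias

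*Protocol*

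**What the plan says.** **Entry.** Section 4.1.2 requires "Clinical decision made to initiate treatment with pazopanib prior to enrollment in the study, but within 30 days of enrollment". It does not require enrolment to come before the first dose. Table 1, footnote a, provides for the opposite order: "Only for patients who have received their first dose within 30 days prior to enrollment". The baseline data in Section 7.1.1 include dose changes since the start of treatment and "Occurrence of any SAEs/AESIs since starting pazopanib".

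**HRQoL.** Primary objective 4 (Section 2) reads "To evaluate the change in health-related quality of life (HRQoL) relative to baseline in patients treated with pazopanib". Under Section 7.5.2 the questionnaires are completed at baseline and then about every 3 months. Section 7 states "A signed, written informed consent form must be obtained from the patient prior to any study-specific procedures or assessments".

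**Risk factors.** Section 7.1.1 takes performance status and the MSKCC or Heng category at enrolment, if recorded, and Appendix 3 counts prognostic factors at enrolment. Section 7 adds that routine procedures "obtained prior to signing of informed consent should be utilized for determining eligibility and baseline purposes". It does not say that they must precede the first dose.

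**Survival.** Section 7.3.1 gives "Overall survival (OS): defined as the time from first treatment with pazopanib until death due to any cause", and PFS has the same origin. Section 9.2.4.1.1 summarises both by Kaplan-Meier and leaves the detailed censoring rules to the RAP. The title of Table 3 (Section 9.1.1), however, counts the 12 months from enrolment.

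**The concern.** Three time points that ought to coincide can lie up to 30 days apart: first dose, consent, and baseline assessment.

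- **HRQoL.** A questionnaire cannot be taken before consent, so anyone who consents after first dose has an on-treatment reference. FKSI-19 and FACIT Fatigue ask about the past 7 days, so a baseline in week 3 or 4 describes time wholly on drug. Section 1.1 lists diarrhoea, nausea, vomiting and fatigue among the commonest events. The RAP cannot recover a pre-dose score that was never collected.
- **Risk factors.** If the laboratory values or performance status used are post-dose, the strata mix prognosis with early response to treatment. The scores already use two anchors: the time-from-diagnosis factor in Appendix 3 runs to pazopanib treatment, while the factors are counted at enrolment.
- **OS and PFS.** A patient who dies between first dose and consent never enters. If those who do enter are counted at risk from first dose, the interval is guaranteed survival time, and ordinary Kaplan-Meier estimates are too high.

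**Working it through.** **1. The plan's own figure.** Table 3 uses N = z² p(1−p)/d² with p = 0.45 (12-month PFS in VEG105192) and z = 1.96. Rounded up, half-widths of 10, 5, 4 and 3 points need 96, 381, 595 and 1057 patients, exactly as stated. At N = 700 the half-width is 1.96 × √(0.45 × 0.55/700) = 3.69 points; at N = 1000 it is 3.08.

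**2. Model for the survival bias.**
- Constant PFS hazard: λ = −ln(0.45)/12 = 0.0665 per month.
- Longest lag: m = 30/30.4375 = 0.986 month.
- Share enrolled after first dose: f. The documents do not give it; 50-100% is assumed.
- Probability w of being free of the blocking event at entry: (1 − e^(−λm))/(λm) if entry is uniform over 0-30 days, or e^(−λm) if everyone enters at day 30.
- Ordinary Kaplan-Meier then estimates S(12)/[(1 − f) + f·w].

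**3. Progression or death blocks entry.** λm = 0.0656, so w = 0.968 (uniform) or 0.937 (day 30).
- f = 1, uniform: 0.45/0.968 = 0.465.
- f = 0.5, uniform: 0.45/0.984 = 0.457.
- f = 1, all at day 30: 0.45/0.937 = 0.480.

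**4. Only death blocks entry.** This needs a 12-month OS, assumed to be 70%. The death hazard is −ln(0.70)/12 = 0.0297 per month, so w = 0.985 (uniform) or 0.971 (day 30), and 0.45 is divided as before.

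**5. OS itself.** The same formula is applied to assumed 12-month rates of 60%, 70% and 80%.

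| Upward bias at 12 months (points) | f = 0.5, uniform | f = 1, uniform | f = 1, all at day 30 |
|---|---|---|---|
| PFS, only death blocks | 0.33 | 0.66 | 1.34 |
| PFS, progression also blocks | 0.73 | 1.49 | 3.05 |
| OS, assumed 60% | 0.63 | 1.27 | 2.57 |
| OS, assumed 70% | 0.51 | 1.03 | 2.08 |
| OS, assumed 80% | 0.37 | 0.74 | 1.48 |

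Every PFS entry is below the 3.69-point half-width.

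**6. Does delayed entry repair it?** In a simulation of 2000 studies of 700 patients (true PFS 45%, uniform entry, progression or death blocking), ordinary Kaplan-Meier averaged 45.6% at f = 0.5 and 46.5% at f = 1. Delayed entry averaged 44.9% and 45.0%. The standard deviation of the estimate was 1.88 points with either method at f = 0.5, and rose from 1.90 to 2.01 at f = 1.

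**7. HRQoL and risk strata.** No arithmetic is possible. The documents give no HRQoL means, standard deviations or time course, and no share of patients with post-dose values.

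**The case against.** **Silence on delayed entry is not an error.** Kaplan-Meier can be run with delayed entry, nothing in the protocol forbids it, and the analyses are to be fully described in the RAP. This stands: its absence alone is no finding. What the protocol does fix is the origin at first dose, entry at consent, and a baseline questionnaire taken after consent.

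**A reader might infer that PFS is overstated by 1.5 to 3 points.** The documents do not support that as the expected size. No criterion in Sections 4.1.2 or 4.1.3 bars a patient who progressed after first dose, so of the two PFS events only death necessarily blocks entry. The 3-point case also needs every patient to enter at day 30. Because the treatment decision itself must fall within 30 days of enrolment, each would need decision and first dose on the same day and enrolment on the last permitted day.

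**Life expectancy under 12 weeks is excluded,** so a constant hazard probably overstates early deaths. The exclusion also cuts the other way: a treated patient whose outlook falls below 12 weeks before enrolment can no longer enter.

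**A reader might infer that the strata are biased.** Section 7 directs sites to routine pre-consent results, which can be pre-treatment. The strata are therefore only possibly affected.

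**A reader might infer that HRQoL decline is understated.** That presumes that early treatment lowers scores. Early symptom relief would act in the opposite direction, and the documents cannot settle it.

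**The study is descriptive and the bias lies within the half-width.** True, but bias does not shrink as N grows, and precision is the stated ground for N. With a standard error of 1.88 points, a 1.5-point shift would lower nominal 95% coverage to about 87%.

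**Conclusion.** The point holds in a limited form. The firmest part is HRQoL: under primary objective 4, every patient enrolled after first dose has an on-treatment reference, and no rule separates these patients from the rest. The direction and size of the effect cannot be computed.

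The survival bias is upward but modest. With 50-100% enrolled after first dose and uniform entry, 12-month PFS gains about 0.3-0.7 points if only death blocks entry, and about 0.7-1.5 points if selection in practice also removes patients who have progressed. OS gains about 0.4-1.3 points across assumed 12-month rates of 60-80%. These figures rest on constant hazards, an assumed share of late enrolment, an assumed OS, and an analysis that counts patients at risk from first dose. This is an inexpensive improvement to the plan, not a threat to its main conclusions.

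**What to change.** 1. Keep first dose as the time origin for OS and PFS, and enter each patient into the risk set at enrolment. Report how many patients had progression dated before enrolment, since they then contribute no PFS time. At the least, add a sensitivity analysis in patients enrolled on or before first dose.
2. Define baseline laboratory values, performance status and risk category as the last value on or before first dose where one exists, and flag post-dose values.
3. Report HRQoL change separately for pre-dose and post-dose baselines.
4. Report the distribution of the interval from first dose to enrolment.
5. Reconcile the clock in the title of Table 3 with the PFS definition in Section 7.3.1.

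**Cost.** No extra visits or procedures are needed. The pazopanib start date is already collected, but the enrolment date is not in the Section 7.1.1 list and must be available in the analysis data. The HRQoL groups become smaller, on top of the site restriction in Section 7.5.1. Early survival intervals widen slightly, and delayed entry assumes that the timing of enrolment is unrelated to prognosis.
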